3.4.3 Monitoring post-biopsy

For biopsy performed in the ENT clinic, monitoring will be per the ENT surgeon performing the biopsy. If the biopsy is done in Interventional Radiology, the standard clinical recovery procedures for patient safety will apply.

3.4.4 Dose reductions

Bintrafusp alfa doses may be reduced to a 600 mg or 300 mg flat dose per investigator discretion (e.g., for \geq grade 1 hemorrhage due to bintrafusp alfa).

3.5 ASSESSMENTS ON TREATMENT

Upon confirmation of eligibility and successful registration, and following completion of the Screening/Baseline visits, participants will begin treatment with bintrafusp alfa.

Following initial agent administration on Week 1, pre-dose assessments may be performed up to 5 days prior to the day of scheduled administration, except where otherwise noted. Results of all applicable procedures and tests are to be reviewed prior to each scheduled administration. Additional clinical and other appropriate evaluations may be performed as clinically indicated.

Refer to the Study Calendar (Section 3.7) for an overview of all tests and procedures to be conducted during screening/ baseline, on study/ during treatment, upon discontinuation of treatment, and during follow up.

3.6 STUDY INTERVENTION COMPLIANCE

Adherence to the protocol will be verified by reviewing the Medical Administration Record (MAR) section of the medical record, which will serve as source documentation.

3.7 STUDY CALENDAR

Procedure	Screening¹	Baseline²	Week 1	Subsequent Weeks (2N+1)^{3,14}	End of treatment^{4,14}	Post Treatment Follow-up¹⁴	
						Safety⁵	Long Term⁶
Treatment							
Bintrafusp alfa ⁷				X	X		
Assessments							
Histologic confirmation	X						
Height	X						
Medical History and Performance Status	X	X					
Physical Exam (including weight, signs & symptoms, skin assessment)	X	X	X	X	X	X	
Vital signs (including pulse oximetry), weight	X	X	X	X	X	X	
HIV, HCV, HBV	X						
NIH Advance Directives Form ⁸		X					
12-lead EKG	X				X	X	
CBC with differential	X	X	X	X	X	X	
Biochemical profile (acute care, mineral, hepatic panels)	X	X	X	X	X	X	
Coagulation profile (PT, INR, PTT/aPTT)		X					
Troponin I	X						
Creatine kinase (CK/CPK)	X						
CD4 (if indicated)	X						
Lymphocyte phenotype TBNK (T, B, and natural killer cells)	X						
LDH		X					
CRP		X	X	X			
TSH, Free T4, lipase, amylase	X	X	X	X ⁹			
Tumor markers		X			X ¹⁵		
Urinalysis	X	X					
24-hour urine collection (if indicated)	X						
Pregnancy test (urine/serum HCG in WOCBP)	X	X	X	X			

Procedure	Screening¹	Baseline²	Week 1	Subsequent Weeks (2N+1)^{3, 14}	End of treatment^{4, 14}	Post Treatment Follow-up¹⁴	
						Safety⁵	Long Term⁶
Tumor imaging and assessment	X			X ¹⁰			X
PET/CT scans ¹³	X						
Adverse Events			X	X	X	X	
Concomitant Medications		X	X	X	X	X	
Correlative Research Studies (Section 5.1)							
Tumor tissue (biopsy) ¹¹			X	X			
Blood samples ¹²		X		X	X		
Telephone follow-up						X	X

1. Screening evaluations performed within 28 days prior to the first drug administration, unless specified in Section 2.2.2
2. Baseline evaluation performed within 14 days prior to the first drug administration.
3. Every odd numbered week for up to 51 weeks. Allowance for scheduling changes: Brief changes (up to 1 days earlier or up to 3 days later) in bintrafusp alfa administration and indicated evaluations may occasionally be required due to travel delays or restrictions, airport closure, inclement weather, family responsibilities, security alerts, government holidays, complications of disease not attributable to disease progression or protocol therapy, etc. These delays will not be considered protocol deviation. The timing of subsequent bintrafusp alfa administrations will be adjusted to maintain a minimum interval of 11 days between bintrafusp alfa administrations. Any dose that cannot be accommodated within this window will be skipped and the dose not made up. In the event of a durable PR or CR after one year on trial, further treatment may be held (even if a total of 26 doses has not been given) and scheduled assessments may be performed at 3-month (+/- 2 weeks) intervals at the discretion of the investigator.
4. End of Treatment visit (EOT): within 14 days of the decision to discontinue treatment prematurely before completion of 26 doses. Clinical Center clinic visit preferred; if the participant cannot return to the Clinical Center for this visit, a request will be made to collect required clinical labs (specify as needed) from a local physician or laboratory. If this is not possible, participants may be assessed by telephone/email for symptoms. Does not need to be completed if drug is withheld after 26 doses.
5. 28 days (+/- 7 days) following last treatment. Clinical Center clinic visit preferred; if the participant cannot return to the Clinical Center for this visit, they may be assessed by telephone/email for adverse events.

6. Subsequent Post-treatment follow-up: Every 3 months (+/- 2 weeks), starting after the safety visit for the first year, followed by every 6 months (+/- 4 weeks) for years 2-5, and then annually (+/- 6 weeks) thereafter at the discretion of the investigator. Follow-ups may be done by phone/email or by clinic visit at the discretion of the investigator. Follow-up via telephone/email will include survival, adverse events, and assessment of further tumor therapy; furthermore, routine outside blood, urine, and imaging results may be collected and used for analysis at the discretion of the investigator. Any other evaluations and tests should be performed as clinically indicated. Participants who have not progressed on treatment will be scanned until progression. Those that completed the previous 26-doses course and have progression will be invited for an additional course (26 doses) at the time of progression.
7. Bintrafusp alfa administered IV at flat dose of 1,200 mg.
8. As indicated in Section **12.3**, all subjects will be offered the opportunity to complete an NIH advance directive form. This should be done preferably at baseline but can be done at any time during the study as long as the capacity to do so is retained. The completion of the form is strongly recommended but is not required.
9. Every 6 weeks.
10. Imaging (Section **6.3**) will be performed every 8 weeks (+/- 1 week). In the event of a PR or CR, tumor imaging assessments may be performed every 3 months (+/- 2 weeks) at the discretion of the investigator. Tumor assessment should be continued beyond end of treatment in participants who have not experienced PD until they experience PD in order to assess PFS. Additional imaging to be performed at the investigator's discretion. Imaging performed in outside facilities maybe utilized in the case of travel restrictions or delays, airport closures, inclement weather, family responsibilities, security alerts and government holidays, etc. Nuclear bone scan or imaging may be done for individuals with known/suspected bone lesions at screening; in these cases bone scans should be done in follow-up for response assessments.
11. Optional biopsies: at baseline (within 2 weeks prior to first treatment) and within 2 weeks of first imaging restaging; optional biopsy at/near progression, where clinically feasible.
12. Where feasible, blood samples for Correlative Research Studies (see Section **5**) will be collected at baseline, W1, W3, W9, and at the EOT. Collection can occur +/- 3 days for any specified timepoint. May also be collected at restaging visits/at time of biopsies per PI discretion.

Where feasible, samples for PK analysis/ADA will be drawn prior to infusion on W1, W3 and W9 and/or with EOT labs if participant comes off treatment prior to any of these timepoints.

13. PET/CT (FDG or Dotatate) scans will be done at screening and at the time of first treatment response evaluation (w8). Then a third one at/near radiographic progression (if there is progression). Effort will be made to keep the same PET/CT type, depending on logistics and availability.

- 14.* Any visits for which administration of trial medication is not planned such as treatment held for AEs, EOT and post-treatment follow-up, assessment may be a telehealth (remote) visit with a member of the study team (e.g., if the patient is not able to return to the NIH CC). Remote visits will be conducted in compliance with NIH guidelines and FDA regulations. A patient may be referred to their local provider or asked to come to the NIH CC for an in-person assessment, if clinically indicated, and at the discretion of the PI. In the case of any visits with participants' local providers, records will be requested. Labs may be drawn locally (interlaboratory variability is not a concern, as these are routine, standardized laboratory tests).
- 15.* Tumor markers (Chromogranin and Neuron Specific Enolase) to be drawn with each restaging.

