3.4.2 Dose delay

- Bintrafusp alfa should be withheld for Grade \geq 2 epistaxis or any Grade \geq 2 toxicity possibly attributed to the study agent until resolution to Grade \leq 1 unless the toxicity in the opinion of the investigator is not clinically relevant or can be medically managed with minimal risk to the participant. Should a clinically relevant grade 2 or 3 toxicity persist for more than 4 weeks, consideration should be given to discontinuing treatment at the discretion of the investigator.
- Laboratory abnormalities which are clinically non-significant and/or unrelated to the agent in the judgement of the investigator, will not lead to dose delays.
- Grade 3 fatigue, headache, nausea, emesis that resolve to Grade \leq 1 with appropriate medical management will not lead to dose delays.
- Management recommendations for infusion-related adverse reactions are found in **Appendix B**: Recommendations for Management of IRRs and AEs, Table A Management of Infusion-related Reactions and should be followed along with institutional standards.
- Immune-related adverse reactions (irAE) should lead to treatment modifications and management per the summarized NCCN recommendations found in **Appendix B**: Recommendations for Management of IRRs and irAEs, Table B Management of immune-related adverse events. Investigators may refer to the relevant guidelines available by ASCO (62), SITC (63), NCCN (64), and ESMO (65).
- For non-medical logistical reasons, unrelated acute illnesses, or palliative radiation, scheduled assessments and dosing can be delayed up to 2 months. Following this interval treatment may resume, and where at all possible, dosing should be restarted to keep in line with the original treatment schedule.

- Local tumor flare phenomenon defined as local pain, irritation, or rash localized at sites of known or suspected lesions will not be considered adverse event or lead to dose interruptions.

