6.3 RESPONSE ASSESSMENT

For the purposes of this study, during the study participants should be re-evaluated for response every 8 weeks (+/- 1 week), according to the [Study Calendar](#).

The Investigator may perform scans in addition to a scheduled trial scan for medical reasons or if the Investigator suspects PD.

Tumor assessments may include the following evaluations: physical examination (with photograph and measurement of skin lesions, as applicable); cross-sectional imaging using computed tomography (CT) or magnetic resonance imaging (MRI) scan of the skull base, neck, chest, abdomen, and pelvis; nuclear bone scan for subjects with known/suspected bone lesions; and CT of the skull base and MRI of brain (at baseline and follow ups as clinically warranted based on symptoms/findings per investigator discretion). The preferred method of disease assessment is CT with contrast. If CT with contrast is contraindicated, CT of the chest without contrast and MRI scan of the skull base, neck, abdomen/pelvis is preferred.

Radiologic imaging: Brain MRI/CT at the baseline and if needed at follow ups. CT scan of skull base, neck, chest, abdomen, and pelvis. or MRI.

In addition, PET (FDG or Dotatate) scan will be acquired at the time of first treatment response evaluation, and at/near radiographic progression, where clinically feasible. PET scan may also be acquired per investigator discretion to characterize metabolic activity of lesions (target/non-target/new) beyond cross-sectional measurement-based response categories, such as in cases of, discordant response among lesions, durable partial response, or other indeterminate radiological changes.

For each participant, the Investigator will designate 1 or more of the following measures of tumor status to follow for determining response: CT or MRI images of primary and / or metastatic tumor masses, physical examination findings, and the results of other assessments.

The measure(s) to be chosen for sequential evaluation during the trial have to correspond to the measures used to document the progressive tumor status that qualifies the subject for enrollment.

Post-baseline response assessments should follow the lesions identified at baseline. The same modality of assessment (e.g., CT) used to identify/evaluate lesions at baseline should be used throughout the course of the study unless subject safety necessitates a change (e.g., allergic reaction to contrast media).

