To assess the primary endpoint of objective response, tumor lesions will be categorized at baseline to target and non-target lesions and used for comparison with subsequent measurements according to the international criteria proposed by the revised Response Evaluation Criteria in Solid Tumors (RECIST) guideline (version 1.1).[\(1\)](#)

All available images collected during the trial period will be considered. Results for the evaluations will be recorded with as much specificity as possible so that pre- and post-treatment results will provide the best opportunity for evaluating tumor response.

Per RECIST 1.1 initial disease progression should be confirmed by imaging after 4 to 6 weeks (preferably 6 weeks, but not later than 8 weeks).

Per RECIST 1.1 any CR or PR should be confirmed by a repeat imaging assessment no sooner than 4 weeks (preferably at the scheduled 6-week interval). Participants who obtain a confirmation scan do not need to undergo the next scheduled imaging assessment if it is due <4 weeks later; imaging may resume at the subsequent scheduled timepoint.

If progression is based on the occurrence of a new lesion in an area not scanned at Baseline, a further on-study scan 6 weeks later should be considered before performing the 28-Day Safety Follow-up visit.

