10.2 SAMPLE SIZE DETERMINATION

There is no published literature on the anticipated efficacy of any specific treatment for participants with ONB. In these rare participants, the objective will be to determine if a modest response rate is possible while keeping the study size small. Thus, in immune checkpoint-naïve participants, this trial will be conducted using a Simon optimal two-stage phase II trial design (Simon R, Controlled Clinical Trials 10:1-10, 1989) to rule out an unacceptably low response rate (CR+PR) of 5% ($p_0=0.05$) in favor of an improved response rate of 20% ($p_1=0.20$). With $\alpha=0.10$ (one sided alpha; equals two-sided alpha = 0.20; probability of accepting a poor treatment=0.10) and $\beta=0.20$ (probability of rejecting a good treatment=0.20), the first stage will enroll 12 evaluable participants, and if 0 of the 12 has a response, then no further participants will be accrued. If 1 or more of the first 12 participants has a response, then accrual would continue until a total of 21 evaluable participants have been treated. As it may take up to several months to determine if a participant has experienced a response, a temporary pause in the accrual may be necessary to ensure that enrollment to the second stage is warranted. If there are 1-2 participants with a response out of 21 participants, this would likely be an uninterestingly low response rate. If there were 3 or more of 21 (14.3%) who experienced a response, this would be sufficiently interesting to warrant further study in later trials. Even if there are fewer than 3 responses, this will provide information on degree of efficacy of a single agent in a rare disease where there is currently no published

information. Under the null hypothesis (5% response rate), the probability of early termination is 54.0%.

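### Imaging may widen to every 3 months at a first, unconfirmed PR or CR, and the confirmation window does not fit the 8-week schedule, so a true response could go uncounted

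*Combined protocol and SAP*

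**What the plan says.** Section 6.3 sets the regular schedule: "participants should be re-evaluated for response every 8 weeks (+/- 1 week"). Footnote 10 of the Study Calendar (Section 3.7) repeats the 8-week interval and then relaxes it: "In the event of a PR or CR, tumor imaging assessments may be performed every 3 months (+/- 2 weeks"), at the investigator's discretion. The word *confirmed* does not appear in that trigger. Footnote 3 of the same calendar also permits 3-monthly assessments, but on a different trigger: a durable PR or CR after a year on trial.

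On confirmation, Section 6.3 asks for repeat imaging of any CR or PR "no sooner than 4 weeks (preferably at the scheduled 6-week interval"). It adds that a participant who has had a confirmation scan may omit the next scheduled one if that is due less than 4 weeks later. It gives a latest time for confirming progression but none for confirming response. Section 6.3.4 and Appendix C make best overall response depend on confirmation at 4 weeks or more.

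Section 10.2 sets the decision rule for the checkpoint-naïve cohort: stop if there are no responses in 12, otherwise continue to 21 and regard 3 or more responses as worth further study.

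**The concern.** Three provisions that govern the timing of the primary endpoint do not fit together. The interval may widen on the strength of a first PR or CR, before the scan that makes it count. The preferred confirmation time refers to a scheduled 6-week imaging interval, but imaging is 8-weekly; the only 6-weekly items are certain laboratory tests (footnote 9) and skin checks (Appendix B). And because confirmation of response has no upper limit, a 3-month scan satisfies the text.

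An investigator can therefore comply with footnote 10 and hold the next scan 11 to 15 weeks after a first PR. If progression shows at that scan, the PR was never confirmed and best overall response is not PR. On a rule of 3 in 21, one lost response can reverse the conclusion. The error runs towards missing activity rather than towards a false claim of it, and whether it occurs depends on which provision the investigator follows.

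**Working it through.** **1. The plan's own design (Section 10.2).** Inputs: p0 = 0.05, p1 = 0.20, one-sided alpha 0.10, beta 0.20; 0/12 stops, at least 3/21 succeeds.

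- Probability of early termination under p0 = 0.95^12 = 0.540, as stated (54.0%).
- P(success | p) = Σ over x = 1 to 12 of C(12,x) p^x (1−p)^(12−x) × P[Bin(9,p) ≥ max(0, 3−x)].
- At p = 0.05 this is 0.080; at p = 0.20 it is 0.803. The design reproduces, with 0.3 points of power above the 80% target.

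**2. Gap from first response to next scan.** Regular schedule: 8 weeks (7 to 9). Footnote 10: 3 months, about 13 weeks (11 to 15).

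**3. Chance of success by confirmation time.** The documents give no response duration, so these inputs are assumptions: 25% respond at first scan; duration is exponential with median m weeks (4, 6 and 12 months = 17.3, 26 and 52 weeks); all responders are switched and none has a separate confirmation scan. The 25% is chosen so that 8-week confirmation at a 6-month median gives about the 20% in the design.

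Share still in response at t weeks = 2^(−t/m). Confirmed rate = 0.25 × share, which goes into the formula in step 1.

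| Median duration | Scan at | Share | Confirmed rate | P(success) |
|---|---|---|---|---|
| 4 months | 8 weeks | 0.726 | 18.2% | 74.3% |
| 4 months | 13 weeks | 0.595 | 14.9% | 60.3% |
| 6 months | 8 weeks | 0.808 | 20.2% | 80.9% |
| 6 months | 13 weeks | 0.707 | 17.7% | 72.5% |
| 6 months | 15 weeks | 0.670 | 16.8% | 68.8% |
| 12 months | 8 weeks | 0.899 | 22.5% | 86.6% |
| 12 months | 13 weeks | 0.841 | 21.0% | 83.2% |

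**4. Partial use of the option (6-month median).** With a fraction f switched, confirmed rate = 0.25 × [(1−f) × 0.808 + f × 0.707]. For f = 0.25 this is 19.6% and success is 79.0%; for f = 0.5 it is 18.9% and 77.0%.

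**5. Cross-check anchored on the protocol's 20%.** Treat 20% as the rate confirmed at 8 weeks and multiply by 2^(−(13−8)/m), taking 3 months as 13.04 weeks. For medians of 3, 6, 9 and 12 months the confirmed rate is 15.3%, 17.5%, 18.3% and 18.7%. Power is 62.4%, 71.8%, 74.7% and 76.2% with all switched, and 72.4%, 76.3%, 77.7% and 78.3% with half switched, against 80.3% with none.

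**6. Dating of progression in switched responders.** Half the scan interval gives a mean delay of 8/2 = 4 weeks against 13/2 = 6.5, a difference of 2.5. The exact exponential form, I/(1−e^(−λI)) − 1/λ with λ = ln 2/m, gives 4.1 against 6.9 weeks at a 6-month median, a difference of about 2.7.

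**The case against.** The strongest reply is that Section 6.3 already asks for confirmation. Footnote 10 refers to that section, is permissive, allows additional imaging, and cancels nothing. Section 6.3 plainly foresees a confirmation scan off the regular schedule. An investigator who follows its stated preference confirms at about 6 weeks, where the same model (6-month median) gives 2^(−6/26) = 0.852, a confirmed rate of 21.3% and an 83.9% chance of success, better than at 8 weeks. This stands. A loss needs two things together: an early switch and no separate confirmation scan. The figures for all responders switched are therefore a worst case.

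A reader might infer that confirmation hangs on a 6-week visit that does not exist. The text does not say that. Four weeks is the rule and 6 weeks a preference, and dosing visits every 2 weeks offer occasions for a scan. What is missing is a 6-week imaging interval, and that mismatch alone leaves no response unconfirmed.

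A reader might also join this to Section 3.4.2, where "scheduled assessments and dosing can be delayed up to 2 months". That allowance is limited to non-medical logistics, unrelated acute illness and palliative radiation, applies to everyone, is not linked to footnote 10, and enters none of the numbers above.

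Finally, DOR and PFS are descriptive Kaplan-Meier endpoints in a single-arm trial, with no comparator to bias, and follow-up after treatment is itself at 3 to 6 months.

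What the reply does not remove is that the trigger omits confirmation, the preferred interval is not on the schedule, and a 13-week scan would still meet the text.

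**Conclusion.** The point holds as a gap in wording that touches the primary endpoint. The plan permits an 11 to 15 week gap before a response is confirmed, and a response that ends in that gap is not counted. In the worst case the chance of success at 13 rather than 8 weeks is lower by 14.0 points at a 4-month median (74.3 − 60.3), 8.4 at 6 months (80.9 − 72.5) and 3.4 at 12 months (86.6 − 83.2); with half switched at 6 months it is lower by 3.9 (80.9 − 77.0). All of this rests on the assumed 25% rate and exponential duration, neither of which is in the documents.

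The stronger reading, that the plan does lower the response rate and power and does lengthen DOR and PFS, is not supported. It could do so, depending on how the discretion is used. The later dating of progression is about 2.5 to 2.7 weeks on average among switched responders, and the fix removes only part of it, because confirmed responders may still move to 3-monthly scans.

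**What to change.** 1. Footnote 10: allow 3-monthly imaging only after a **confirmed** PR or CR, and reconcile this trigger with the one in footnote 3.
2. Section 6.3: replace the 6-week reference with *at 4 weeks or later and no later than the next scheduled 8-week scan*. State also whether a confirming scan obtained later than that still counts.

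The cost is two wording changes and at most one scan for responders who would otherwise have been switched early. That scan is already on the 8-week calendar: 52/8 = 6.5 scans a year, within the 7 CT scans a year counted in Section 12.5.1.3. The 3-monthly option remains available once the response is secure.
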